8. SECONDARY EFFICACY ANALYSES

Key secondary outcomes included depression-free days and health care costs.

Depression-Free Days

The prespecified secondary outcome will be cumulative depression-free days based on the 10-item Center for Epidemiologic Studies Depression (CESD-10) scale, a non-diagnostic, epidemiologic, reliable and valid measurement for depressive symptoms, measured at baseline, 6-months, 12-months, and 18-months in all 3 arms. *Depression-free days* will be calculated by using linear interpolation to estimate daily depression severity at each of the four assessment time points for the 3 study arms. Depression-free days is a valid and easily interpretable measure for estimating depression treatment outcomes when multiple measures of depressive symptoms occur over time. This measure is also amenable to cost-effectiveness analyses. In other trials, Depression-free days have been calculated using intervals as long as 6 months. While a shorter interval (e.g., 3 months) can provide a more precise assessment of cumulative depressive symptoms over time, a 6-month interval was selected so as to avoid frequent

communication between the study team and study participants. More frequent assessments could lead to increased behavioral support and could cloud the interpretation of the No Depression Screen group which was not intended to receive any behavioral interventions.

An epidemiologic instrument was chosen over a clinical measure of depressive symptoms as the use of a clinical measure would have mandated referral for depression treatment in those who screened positive in the No Screen group. The CESD-10 is a short version of the original 20-item scale. The scores range from 0 to 30. A score 4 or greater has been found to be the optimal cutpoint for a positive depression screen with a sensitivity and specificity of 97% and 84%, respectively, compared to a psychiatric interview in a sample of older adults. Based on a review of the literature, we inferred that a cutpoint of 10 on the 10-item CESD would represent clinically significant depressive symptoms. 10

The following rule will be used to convert CESD score to depression day

CESD < 4 -> 0 depression day

CESD = 4 -> 1/7 depression day

CESD = 5 -> 2/7 depression day

CESD = 6 -> 3/7 depression day

CESD = 7 -> 4/7 depression day

CESD = 8 -> 5/7 depression day

CESD = 9 -> 6/7 depression day

CESD >= 10 -> 1 depression day

Health Care Costs and Lost Productivity

The other prespecified secondary outcome will be Health Care Costs and Lost Productivity. 1 At baseline, 6-months, 12-months, and 18-months, patients will report measures of economic productivity, including employment status, occupation, hours spent at work, and time lost from work for health-related reasons.11 At 6-months, 12-months, and 18-months, patients will also report healthcare utilization since their last intake assessment, including emergency department (ED) visits, hospitalizations (location, admission and discharge dates), psychiatric medication use, name and dose, ambulatory care visits with mental health specialists, cardiologists, as well as PCPs and finally hospitalizations for cardiovascular events. Patient self-reports of healthcare utilization will be supplemented by review of the EMR and claims systems to collect data on healthcare utilization during the 18-month trial period. Average Medicare reimbursement rates according to diagnosis-related groups will be applied to inpatient visits to estimate hospitalization costs, and the Medicare physician fee schedule will be applied to outpatient and ED resource use according to current procedural terminology codes. Costs of study depression treatment will also be incorporated into estimates of healthcare utilization costs for those assigned to the Screen, Notify, and Treat group who agree to depression treatment by study personnel. To estimate economic costs from a societal perspective, changes in productivity and time spent traveling to appointments will also be accounted for. Costs will be standardized across years using the U.S. Consumer Price Index and presented in U.S. dollars.12

-

¹Cost of health care utilization was erroneously listed as a co-primary outcome on the initial clinicaltrials.gov entry. This error was corrected in clinicaltrials.gov on October 25, 2017, prior to completion of data collection or any interim data analyses. As can be seen in the planned statistical analyses, the sample size for the study was driven entirely by the change in QALYs outcome. Cost-effectiveness analyses, in contrast, were never intended to be listed as a co-primary outcome as they were not guided by economic hypotheses involving statistical tests and sample size calculations for incremental cost-effectiveness ratios were never attempted.

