#### **Outcomes**

Quality-adjusted Life Year Assessment (Primary). Following the precedent set by RCTs with other depressed medical populations, we chose the Short Form Health Survey (SF-12) questionnaire to assess health related quality of life for the economic analysis. The SF-12 uses Likert scales to assess health-related quality of life aspects that are most directly relevant to depressed post-ACS patients: mobility and physical activities, ability to self-care, ability to perform usual activities, pain, and anxiety/ depression. Extensive validation, including construct validity, published normative data, and sensitivity to change have all been published for this scale. It has been used extensively the cost-effectiveness of a screening or intervention practice, and has successfully been used in depression interventions with other patients, allowing comparability with other data and settings. It is ideal for using in mail or web surveys, and takes less than 5 minutes. The NICE group in Britain recommends its use for providing cost and QALY data. We will collect deaths/dates of death from the national death index & EMR.

**Depression Symptom Assessment**. The AHA advisory suggests using the PHQ-2 (yes-no version) first, and then the full PHQ-8 for the assessment of depression symptom severity. In CODIACS QoL we will not utilize the PHQ-2, and instead ask all 8 items of the PHQ-8. The PHQ-8 has excellent psychometric properties, including sensitivity to successful change from treatment, good test-retest reliability when no treatment is offered, construct validity, reasonable correlations with health-related quality of life measures, and the ability to approximate likelihood of a major depressive

disorder. Scores on the PHQ-8 range from 0- 24 and a score of ≥10 is used for detecting likely depressive disorder, and clinically significant depression levels.

**CES-D10.** The Center for Epidemiologic Studies Depression Scale (CESD) is a screening measure (NOT a diagnostic tool) developed to identify current depressive symptomatology related to major or clinical depression in adults and adolescents. The CES-D10 is a short version of the original 20-item scale. The scores range from 0 to 30, and a score of 10 or greater is considered significant.

**Depression-free Days.** These will be calculated by using linear interpolation to estimate daily depression severity from the CES-D10 obtained at each of the four assessment points for all groups.

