5.3 Primary Efficacy Analysis

Change in QALYs from baseline through 18 months post-randomization will serve as the primary outcome for this trial. QALYs were chosen as the primary outcome to facilitate comparisons of the effect of depression screening with other preventive interventions as well as to facilitate cost-effectiveness analyses and policy decisions. As QALYs do not directly assess depression, this outcome measure also minimized possible patient reporting bias as a result of lack of participant blinding or masking to condition. The goal of the primary analysis is to identify whether there is difference in the change in QALYs among the three groups. QALYs describe the duration of illness per years of survival, adjusted for quality of life experienced during that survival. One year in perfect health is equivalent to 1 QALY. All patients will complete a standardized measure of quality of life using the Short Form-12 Health Survey, Version 2™ (SF-12) at baseline, and again at 6-months, 12-months, and 18-months. 1 QALYs will be estimated from the SF-12 using the Short Form 6 Duration (SF6D) which converts data from 7 items in the SF-12 assessing 6 domains (physical functioning, role limitations, social functioning, pain, mental health and vitality) to QALYs.2 Study patients who die during the study period will be assigned a utility score of 0 for assessments after the date of death. QALYs over 18 months will be calculated as the area-under-curve by interpolating linearly the scores at the four assessments (baseline, 6-month, 12-month, 18-month). There were no data obtained or available for these measures between assessments. Change in QALYs will then be obtained by subtracting the QALYs that would have occurred if there was no change in the baseline utility score from the actual QALYs that were measured across 18 months. The analysis will follow the principle of intention-to-treat and will be conducted on each imputed dataset with the point

estimate deriving from the average of 5 datasets and the pooled variance calculated using Rubin's formula.

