5.6 Missing Data

CESD-10 questionnaire with missing data will be prorated if that participant answered more than 7 items. The missingness of data will then be assessed using Little's test. If data are found to missing at random, we will perform multivariated imputations to generate 5 imputed datasets by basing on covariates which were predictive of missing pattern such as input from prior visit and site variable; random sampling was used to impute the missing values at baseline. Missing data will be imputed sequentially, starting with the baseline visit, then the 6-month visit, followed by the 12-month and 18-month visits.

In sensitivity analyses, missing data will be handled by carrying the last observed value forward and by using best case-worst case scenario – in best case, we assumed that all missing had perfect health. In worst case scenario, we assumed all missing data had worst health status (QOL = 0).

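### Depression-free days has no rule for death, so the SAP's missing-data rules, read literally, can credit depression-free days to patients after they have died

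*SAP*

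**What the plan says.** SAP section 8 defines the outcome: "The prespecified secondary outcome will be cumulative depression-free days based on the 10-item Center for Epidemiologic Studies Depression (CESD-10) scale". This count "will be calculated by using linear interpolation to estimate daily depression severity at each of the four assessment time points for the 3 study arms", and a table then turns each score into a fraction of a depression day, from "CESD < 4 -> 0 depression day" to "CESD >= 10 -> 1 depression day". The Protocol (Outcomes, Depression-free Days) gives the same construction: "linear interpolation to estimate daily depression severity from the CES-D10 obtained at each of the four assessment points for all groups". Neither place mentions death.

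The only rules for death concern the primary outcome. SAP 5.3 states: "Study patients who die during the study period will be assigned a utility score of 0 for assessments after the date of death". The Protocol (Statistical Methods, Hypothesis 1) gives zero QALYs from death to the end of follow-up. SAP 7.2 compares mortality between groups as a separate item.

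SAP 5.6 opens with proration of incomplete CESD-10 forms. If the data are found to be missing at random, it then calls for five imputed datasets: "Missing data will be imputed sequentially, starting with the baseline visit, then the 6-month visit, followed by the 12-month and 18-month visits". LOCF is a sensitivity analysis. The section does not set apart visits that are missing because the patient has died. SAP 4.2 specifies an intent-to-treat sample, so patients who die stay in the analysis.

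**The concern.** Depression-free days needs a score at all four assessments. For a patient who dies, the later scores do not exist, and the only instruction in the plan for absent scores is to fill them in from earlier visits. Time not lived can then count as benefit on a key secondary outcome, while the primary outcome gives death a zero.

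Death is foreseeable here. Patients are enrolled 2 to 12 months after an acute coronary syndrome and followed for 18 months. The Protocol's background section also puts the risk of recurrent events and death at about double in depressed patients, so death is related to what this outcome measures. Different analysts could impute, truncate at death, or drop the deaths, and each could claim to follow the SAP.

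**Working it through.** **The plan's own figures.** The documents give no expected mortality and no effect or standard deviation for depression-free days. The nearest figure is the QALY sample size of 475 per group. It reproduces: 2 × (1.960 + 0.842)² × (0.17/0.031)² ≈ 472, or 473 with the t-distribution. No depression-free-day quantity enters it.

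**Inputs from the SAP.** The window is 18 months, about 548 days. The section 8 table is equivalent to a depression fraction of (s − 3)/7 for a score s from 3 to 10, with 0 below that and 1 above. The depression-free fraction is f(s) = 1 − (s − 3)/7, so f(3) = 1, f(5) = 5/7, f(7) = 3/7 and f(10) = 0.

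**Assumptions, not in the documents.** Scores stay constant before and after death, deaths are spread evenly over follow-up, and mortality is 1–5% per arm.

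**Step 1: can the QALY rule be borrowed?** No. A utility of 0 is the lowest value the plan assigns. A CESD-10 score of 0 is the best score and earns the maximum of depression-free days. The best-case and worst-case analyses in SAP 5.6 are stated as perfect health and QOL = 0, with no CESD-10 value. This outcome needs its own rule.

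**Step 2: one patient who dies at day 274.** Remaining days: 548 − 274 = 274. Credit after death = 274 × f(s).

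| Score, filled in | Full 18 months | Counted to death | Credited after death |
|---|---|---|---|
| 3 | 548 | 274 | 274 |
| 5 | 391 | 196 | 196 |
| 7 | 235 | 117 | 117 |
| 10 or more | 0 | 0 | 0 |

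**Step 3: shift in an arm mean.** With evenly spread deaths the average remaining time is 548/2 = 274 days, so the average credit per death is about 117 to 274 days for scores 7 to 3. Multiplied by mortality:
- lowest: 0.01 × 117 = 1.2 days
- highest: 0.05 × 274 = 13.7 days

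**Step 4: distortion of the difference between arms.** With similar filled-in scores in both arms this is the credit per death times the difference in mortality. Per percentage point it is 0.01 × 117 = 1.2 to 0.01 × 274 = 2.7 days. If 70–80% of the filled-in days are depression-free, the credit per death is 274 × 0.70 = 192 to 274 × 0.80 = 219 days, or 1.9 to 2.2 days per point. The arm with more deaths receives the larger credit.

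**Step 5: how large could the mortality difference be?** Take 5% mortality overall, 20% with elevated symptoms (SAP 5.4) and doubled risk in that 20%. Mortality in the rest is 0.05/(0.8 + 0.2 × 2) = 4.2%. If treatment removed all the excess, the arms would differ by 0.2 × 4.2 = 0.83 points, or about 1.6 to 1.8 days, against the intervention. At 3% mortality it is 0.2 × 2.5 = 0.5 points, about 1 day. Chance alone is of similar or greater size: with 500 per arm and 5% mortality, the standard error of the difference is √(2 × 0.05 × 0.95/500) = 1.4 points, or about 3 days. For scale, if 20% of an arm gained 50–100 days each (also an assumption), the benefit would be 0.20 × 50 = 10 to 0.20 × 100 = 20 days.

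**The case against.** SAP 5.6 never says that a visit after death counts as missing. Imputation depends on a missing-at-random finding. SAP 5.3 ties the imputed datasets to the primary analysis, and section 8 does not mention them. This is fair, and it limits the claim to what the text permits when read literally. It does not close the gap: 5.6 names the CESD-10 in its first sentence, LOCF would act in the same way, and if neither applied there would be no stated way to score patients who die.

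The assumptions also pull against each other. If deaths concentrate in depressed patients, their earlier scores are high, the filled-in scores will be high, and the credit shrinks, to nothing at 10 or more. This stands, so no single figure per death is secure. Terminal illness is an exclusion, so mortality may be low.

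A reader might infer that cost-effectiveness results would be misled, because section 8 calls the measure suitable for such analyses. The documents do not support that: the planned ratio (Protocol, Hypothesis 2) divides by the difference in QALYs, which have a death rule, and no cost per depression-free day is specified.

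Finally, counting zero after death treats a dead day like a fully depressed day. Scoring only time alive is also defensible. That is a reason to state the choice.

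**Conclusion.** The gap is real and should be closed. Neither document says how death enters depression-free days, and the missing-data rules taken literally can score patients as depression-free after death.

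Under the stated assumptions (1–5% mortality, evenly spread deaths, constant scores of 3 to 7) arm means rise by about 1 to 14 days. A reader might take that as bias in the treatment comparison. It is not: with equal mortality and similar filled-in scores it largely cancels. The distortion between arms comes mainly from a difference in mortality, at roughly 2 days per percentage point. On the scenarios above that is about 1 to 3 days, modest against an assumed benefit of 10 to 20.

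It would also be too strong to say that every death earns a full 18 months of depression-free days. The full window is scored, but the days credited after death run from none to all of those remaining. The primary analysis, the sample size and the planned cost-per-QALY ratio are not affected.

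**What to change.** In SAP section 8, state that no depression-free day is counted after the date of death, and state how the interval from the last assessment to death is scored. Carrying the last score forward is one option; the documents do not settle it. In SAP 5.6, restrict CESD-10 imputation and LOCF to visits at which the patient was alive. Add a supportive analysis of depression-free days as a proportion of days alive.

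The cost is a few sentences and one programming condition. The Protocol (Outcomes) already provides for collecting dates of death. Arm means will be slightly lower. Zero days after death makes the outcome partly a composite with mortality; the days-alive analysis shows how much of any difference comes from that.

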In a secondary analysis, we will use a mixed model with a random intercept to assess the change in quality of life utilities over time comparing individuals in the AHA Screen, Notify & Treat group vs. the other two randomization groups. This model will incorporate main effects of time (i.e., baseline, and 6-, 12-, and 18-months post-randomization), treatment group, and the time by treatment group interaction. Using this model, we will be able to calculate the mean utility at each follow-up time period for the 3 groups and determine whether the response profile differs by time across groups.

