5.4 Sample Size Determination

The sample size of the trial was determined based on an assumed standard deviation for QALYs of 0.17.5 Additionally, based on a general health-related quality of life outcome in a prior study of management of depression for patients with cancer, we assumed a net improvement in QALYs of 0.155 over 18 months of follow-up for depressed individuals who receive depression treatment in the Screen, Notify and Treat group.6 We assumed a 0.055 gain in QALYs for all patients not directly linked to depression treatment (i.e., those in the No Screen group, the Screen & Notify group and those without elevated depressive symptoms in the Screen, Notify, and Treat group). An important consideration for this trial is that only 20% of patients randomized to the Screen. Notify and Treat group were expected to meet criteria for elevated depressive symptoms and thus, to receive depression treatment. Therefore, assuming an increase in QALYs of 0.21 (0.055 background improvement + net improvement of 0.155) over the 18-month follow-up period for the 20% of patients diagnosed and treated for depression in the Screen, Notify, and Treat group and a 0.055 improvement in QALYs for the 80% of patients in this randomization group without depression, an overall gain in QALYs of 0.086 over the 18 month follow-up period was anticipated in this randomization group (0.21 * 0.2 + 0.055 * 0.8 = 0.086). Thus, we anticipated a difference in QALYs of 0.031 (0.086 change in the Screen. Notify, and Treat group minus 0.055 in the No Screen group or Screen and Notify Group), leading to an expected effect size of 0.18 (= 0.031/0.17). With this effect size, we determined the sample size per group to be 475, which would yield 80% power for a two-sided t-test at 5% level. We chose to determine sample size based on a pairwise comparison at 80% power in the two-step procedure (described above), as a conservative approach relative to powering based on the F-test. Specifically, under the scenario where one group has higher QALY than the other two by an effect size 0.18, the F-test will yield 84% power. Adding in 5% loss to follow-up, we selected an overall sample size of n=500 in each randomization group for an overall sample size of n=1500.

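### Depression-free days, the only planned efficacy analysis of the CES-D10, counts no change within scores 10–30 or within 0–3; a supportive analysis of the full 0–30 score should be prespecified beside it

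*SAP*

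**What the plan says.** SAP section 8 names the outcome: "The prespecified secondary outcome will be cumulative depression-free days based on the 10-item Center for Epidemiologic Studies Depression (CESD-10) scale". It describes the instrument in these terms: "The CESD-10 is a short version of the original 20-item scale. The scores range from 0 to 30". The conversion to depression days starts at "CESD < 4 -> 0 depression day", rises by one seventh per point from 4 to 9, and ends at "CESD >= 10 -> 1 depression day". The Protocol, under Outcomes, describes the same derivation by linear interpolation over the four visits and says of the scale: "The scores range from 0 to 30, and a score of 10 or greater is considered significant".

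No other efficacy analysis of depressive symptoms is planned. SAP section 8 lists the secondaries: "Key secondary outcomes included depression-free days and health care costs". The secondary mixed model in the Protocol under Hypothesis 1 concerns another variable: "we will use a mixed model with a random intercept to assess the change in quality of life utilities over time". The PHQ-8 is collected at 18 months in all arms, but the Protocol's Data Monitoring section uses it as a safety measure.

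On where benefit is expected, SAP section 5.4 says that "only 20% of patients randomized to the Screen. Notify and Treat group were expected to meet criteria for elevated depressive symptoms". The net QALY gain is assumed in that fifth of the arm alone. Neither document gives a test, an effect size or a power figure for depression-free days.

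**The concern.** The patients expected to benefit are selected for elevated symptoms (PHQ-8 of 10 or more), so many of them can be expected to sit at or above the CES-D10 cap of 10. There the outcome is flat: the SAP itself takes 10 as the mark of clinically significant symptoms, and the outcome has no gradation above it. A patient who goes from 20 to 11 at every follow-up visit contributes the same depression-free days as one who stays at 20.

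Depressive symptoms are the direct target of the intervention. If the QALY comparison is null, readers will want to know whether depression failed to improve, or improved without moving QALYs. A null result on a scale that does not register part of the possible improvement cannot separate the two.

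**Working it through.** **1. The plan's own figures.** From SAP 5.4: difference 0.031, SD 0.17, 475 per group, two-sided 5%.
- Standardized difference d = 0.031/0.17 = 0.182. The sample-size formula gives 473 per group for 80% power (stated: 475). At 475, power is 80.2%.
- F-test with one group higher than the other two: noncentrality = 475 × (2/3) × 0.182² ≈ 10.5; power 83.5% (stated: 84%).
- 475/0.95 = 500.

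These reproduce. They concern QALYs only; there is no CES-D10 figure to reproduce.

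**2. The conversion rule.** For whole scores it equals min(1, max(0, (score − 3)/7)). Scores 0–3 (4 values) and 10–30 (21 values) are flat, that is 25 of the 31 possible scores. Points of improvement that still register:
- 20 to 11: 0 of 9
- 18 to 10: 0 of 8
- 14 to 8: 2 of 6 (33%)
- 16 to 6: 4 of 10 (40%)
- 14 to 4: 6 of 10 (60%)
- 12 to 6: 4 of 6 (67%)

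This step needs no assumption.

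**3. Power, on stated assumptions.** Scores were simulated at 0, 6, 12 and 18 months, kept within 0–30, and interpolated linearly. The time-averaged score is the area under that line divided by 18 months: (3·Y0 + 6·Y6 + 6·Y12 + 3·Y18)/18. Depression-free days were computed from the same scores by the rule above. Each standardized difference d was converted to two-sided 5% t-test power with n = 475 per arm, noncentrality d × √(475/2) = 15.41 d.

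Worked example: screen-positives (20%) mean 15, SD 5; others mean 5, SD 3; visit correlation 0.7; background fall of 2 points and a 4-point benefit in screen-positives. Then d = 0.156 for the full score and 0.094 for depression-free days, a ratio of 0.094/0.156 = 0.60. Noncentralities are 2.40 and 1.45; power is 67% and 31%.

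With a 3-point benefit in screen-positives, unadjusted:
- Baseline mean 11: about 58% full score, 45% depression-free days.
- Baseline mean 15, SD 5, background fall of 3 points, others mean 5, SD 3.5, correlation 0.6: 48% and 24%. Adjusted for baseline CES-D10: 97% and 54%.
- Baseline mean 18: about 37% and 10%.

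Repeat runs differ by a few points.

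**4. Where the loss disappears.** Let 25% of screen-positives remit without treatment and 60% with it, a remitted patient scoring like a screen-negative, with screen-negatives at mean 3, SD 2.5. Unadjusted power for the full score and depression-free days is 53% and 55% (screen-positive mean 10), 57% and 57% (mean 11), 61% and 60% (mean 12). Over a wider grid of 72 scenarios (7–20% screen-positive; constant, proportional or remission effects), the ratio of standardized effects, depression-free days to full score, runs from 0.36 to 1.04 unadjusted and 0.31 to 1.00 adjusted. Four of the 72 slightly favour depression-free days, unadjusted.

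The SAP does not say whether scores are converted before or after interpolation. In these simulations the choice moved power for depression-free days by no more than about 7 points and did not change the overall picture.

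**The case against.** Depression-free days is a deliberate, cited choice. SAP section 8 calls it valid and easy to interpret for repeated depression measures, and suited to cost-effectiveness work. It gives sourced reasons for both anchors: 4 as the optimal screening cutpoint and 10 as clinically significant. A patient at 11 is by that definition still depressed, so counting no depression-free days is what the outcome is meant to do. All of this stands, and it is why the measure should stay.

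A reader might infer that improvement in treatable patients is simply thrown away. The documents do not support that: a fall through the 4–10 range counts. Treatment is offered on the PHQ-8, so some treated patients may start below 10 on the CES-D10. The trial also targets patients without prior depression (SAP 4.1), so milder screen-positives, nearer the graded range, are plausible.

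A reader might also infer that the full score always wins by some minimum margin. Step 4 of the working shows it does not.

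Finally, the 18-month PHQ-8 is an uncapped severity score. It helps only in part: it is one time point, is not a planned efficacy comparison, and has no baseline value in the No Screen arm.

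What the objection does not supply is a reason for depression-free days to be the sole efficacy comparison of symptoms.

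**Conclusion.** The point holds in a limited form. It is certain from the documents that depression-free days is the only planned efficacy analysis of the CES-D10 and that it does not register change within 10–30 or within 0–3. It is likely, not certain, that this costs power: it does so when screen-positive patients improve but often remain at 10 or more. Under the assumptions shown, unadjusted power is about 10–45% against 37–58% for screen-positive baseline means of 11–18, and the gap can vanish under full remission with low-scoring screen-negatives. Every one of these power figures rests on assumed CES-D10 means, SDs, correlations and effects, because the documents give none.

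The material does not support replacing or demoting depression-free days, which is a reasoned and already named key secondary. Primary QALY power is untouched. This is a cheap improvement to a secondary analysis, not a defect in the trial's main comparison.

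**What to change.** Keep depression-free days as the named key secondary and for cost-effectiveness. In SAP section 8:

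- Prespecify a supportive between-arm comparison of the time-averaged 0–30 CES-D10 (area under the curve over the four visits divided by 18 months), with a 95% CI and a linear term for baseline CES-D10.
- Add the same baseline term to the depression-free-days comparison.
- Require that any statement that depression did or did not improve report both results.

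The cost is one extra model and one more secondary comparison, on data already collected; no visits or patients are added. Label the new analysis supportive: depression-free days is already named, the SAP was last updated on 1 January 2019, and the Protocol records recruitment as completed, so a late switch of the inferential endpoint would carry a credibility cost.
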